8.3 Populations for Analyses

The reliability analyses will be performed on the intent to treat (ITT) population which consists of all participants who participated in one full round of the study, meaning they have full data on all covariates as well as the volume of fluid administered, the position, and whether or not the sensor triggered. For the rewet testing all data collected will be analyzed.

A per protocol analysis is planned to examine the cases of rewet testing when leakage did not occur.

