5.3 Strategies for Recruitment and Retention

Participants will be recruited from a database in which they have agreed to be contacted for studies or through IRB approved advertising. New participant(s) will be recruited if any participant withdraws from or is unable to complete the study, such that the total number of participants who complete the study are 56.

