5.4 Early Withdrawal and Replacement

Each participant will remain on the study until they have completed up to four simulated urinary void cycles in each of the 3 positions: supine, sitting, and laying on either left or right side or they are withdrawn for any reason. Participants that withdraw or are withdrawn early will be replaced. Fifty-six participants are required to successfully complete the testing. Twenty-two of the 56 participants will also perform the retest testing procedure.

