8.8 Handling of Missing Values

Listwise deletion of observations with missing data is necessary to correctly calculate Cronbach's coefficient alpha and for the chi-square test, therefore listwise deletion will be used for the reliability analysis and chi-square analysis. All missing data will be quantified in the final report and possible biases for any missing data will be reported.

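### Section 8.3 labels a complete-case set intent to treat and non-completers are replaced until 56 finish, so alert tests abandoned, unrecorded or never set up can fall out of the pass rate

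*Combined protocol and SAP*

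**What the plan says.** Section 8.3 assigns the reliability analyses to a population it names intent to treat. That population "consists of all participants who participated in one full round of the study, meaning they have full data on all covariates". The same sentence makes a known volume, a known position and a known alert result further conditions of entry. What counts as a full round (one position or all three) is not defined. For the rewet subset only, 8.1 defines completion as having all data on all three brief tests.

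The replacement rules are open-ended. Section 5.3: "New participant(s) will be recruited if any participant withdraws from or is unable to complete the study". Recruitment goes on in this way until there are 56 completers. Section 5.4 keeps each participant on study until the void cycles are done "or they are withdrawn for any reason", and adds: "Participants that withdraw or are withdrawn early will be replaced". Neither section separates device reasons from personal ones. Section 4.2 also ends the study on a count of completers.

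Section 8.8 states that "listwise deletion will be used for the reliability analysis and chi-square analysis", and promises to quantify missing data and report possible biases. Section 8.9 bases frequencies and percentages on the non-missing sample.

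Sections 4.1 and 6.4.2 score a brief as failed if there is no alert within the five-minute wait following pour three. Section 6.4.1 has staff confirm, before the first pour, that the App shows the Pod as connected. It gives no outcome for a Pod that will not connect.

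**The concern.** An intent-to-treat set keeps everyone who entered, whatever happened next. The set in 8.3 requires the outcome and every covariate to be present, so its name tells the reader the reverse of what it does. Combined with replacement, this means that an alert test begun but not finished can leave the results and be succeeded by a test in a new person who does finish.

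That matters here because the product under evaluation is the whole system of Pod, App, charger and Brief (1.1, 2.2). A fault in any of these that prevents a test is a performance result and should not be treated as a neutral loss. If such faults are left out, the pass percentage describes the system only where it could be tested to the end.

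The plan does deal with this problem for the rewet tests: 4.1 and 6.4.3 say how leakage is classified, and 8.3 analyses all rewet data with a per-protocol analysis alongside. The alert tests, which carry the primary endpoint, have no equivalent.

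**Working it through.** **Step 1. Which events can be lost?**

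| Event in an alert test | Where covered | Effect on the pass rate |
|---|---|---|
| Alert after pour one, two or three | 4.1, 6.4.2 | Pass, kept |
| No alert after pour three, including a Pod that goes silent midway | 4.1, 6.4.2 | Fail, kept, even if the fourth pour suggests a defect |
| Brief or tubing badly placed before the pour | 6.4.1 | Readjusted, test goes ahead |
| Pod cannot be connected at set-up | 6.4.1 requires connection, assigns no outcome | Not scored |
| Test abandoned or result not recorded | Nowhere | Outside the 8.3 set and the 8.9 denominator; a non-completer is replaced |

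Only the last two rows are a gap.

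**Step 2. The plan's own figure.** Section 8.1 gives N = 56 with success proportions of 0.85, 0.90 and 0.95. The Wald 95% half-width at 0.90 is 1.96 × √(0.90 × 0.10 / 56) = 0.079. At N = 64 it is 0.074. The plan states no target width, so 56 can be neither reproduced nor refuted from its stated rule. Nothing below depends on that; 7.9 points serves only as a yardstick.

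**Step 3. Size under assumed losses.** Let x be the passes among n completed tests and k the lost tests scored as failures. The reported rate is x/n and the rate with losses restored is x/(n + k). The shift is (x/n) × k/(n + k). Exact limits are Clopper-Pearson: the 0.025 quantile of Beta(x, n − x + 1) and the 0.975 quantile of Beta(x + 1, n − x), with n + k in place of n where losses are restored. The documents do not give k, so every value is an assumption. The pass counts are whole numbers near the planned 90%: 0.90 × 56 = 50.4, 0.90 × 28 = 25.2, and 0.90 × 168 = 151.2 (56 participants × 3 tests = 168).

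One position, 50 passes among 56 completers:

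| k | Rate | Exact 95% CI | Shift (points) |
|---|---|---|---|
| 0 | 50/56 = 89.3% | 78.1–96.0 | 0 |
| 1 | 50/57 = 87.7% | 76.3–94.9 | 1.6 |
| 3 | 50/59 = 84.7% | 73.0–92.8 | 4.5 |
| 6 | 50/62 = 80.6% | 68.6–89.6 | 8.6 |

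The result depends little on the starting rate. With k = 3, 48/56 = 85.7% becomes 48/59 = 81.4%, and 53/56 = 94.6% becomes 53/59 = 89.8%.

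One side only (28 participants per side in 8.2), k = 2: 25/28 = 89.3% becomes 25/30 = 83.3%.

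All positions pooled, k = 3: 151/168 = 89.9% becomes 151/171 = 88.3%, a shift of 1.6 points.

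**Step 4. Against the yardstick.** At one position, five losses give 50/61 = 82.0%, a shift of 7.3 points, and six give 8.6. It would therefore take five to six device losses at the same position to move the estimate by about the planned half-width of 7.9 points.

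**The case against.** The best defence is that little can be lost. Participants are healthy volunteers seen in one visit of about two hours. A reader might infer that a Pod dropping out during a test vanishes from the results. The documents do not support this: staff record at each five-minute mark whether an alert occurred, and silence after the third pour is a recorded fail. Nor do they tell staff to stop an alert test for lost connection or poor fit.

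Four further inferences also go too far.

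- *Section 5.4 swaps out participants whose briefs fail.* It says that "Fifty-six participants are required to successfully complete the testing", but 4.1 and 6.4.2 move a participant with a failed brief on to the next one, so success there most naturally means finishing.
- *Declining to state sex removes a valid result.* Section 8.6 codes that answer as a category, so it is not missing. Age is checked at eligibility and brief size is recorded by staff, so covariate loss is unlikely, although a blank entry would have this effect under 8.3.
- *The 8.3 set governs the pass percentage.* It is tied to the reliability analyses, and 8.8 confines listwise deletion to those and the chi-square tests. No text expressly removes a replaced participant's finished tests from the percentages. The percentages lose unfinished tests through the non-missing denominator in 8.9.
- *A participant who cannot tolerate the wet brief is a device failure.* That withdrawal does not show whether the sensor would have alerted.

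It also stands that 8.8 promises to quantify missing data and discuss bias, and that 8.4 settles the handling of deviations before analysis. These steps make losses visible. They do not put lost tests back into the rate, and no sensitivity analysis is planned.

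**Conclusion.** The point holds in limited form. The label in 8.3 is wrong on the face of the text, and no rule scores an alert test that is abandoned, unrecorded or never set up, while non-completers are replaced until 56 finish. If such losses come from the device, the pass rate is biased upward, since scoring them as failures can only lower it.

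The size is not known and may be zero. The illustrations rest on assumed loss counts and on scoring every lost test as a failure, so the lower figures are scenarios and not the correct pass rate. For three losses the shift is about 4.5 points if all fall at one position and about 1.6 points pooled over all tests. The pooled figure adds back only the lost tests. If a full round means all three positions, one lost test could also remove that participant's other finished tests from the reliability analyses.

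**What to change.** In 8.3:

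- Define the primary set as every brief test begun, meaning the brief was applied and Pod set-up was attempted, in any enrolled participant, including those later replaced. Starting the set only at a connected Pod or a first pour would leave out set-up connection failures.
- Score a test that cannot be set up or finished because of a Pod, App or brief fault as not passed, and say in advance what counts as such a fault.
- List tests lost for participant reasons with those reasons, and vary their scoring in a sensitivity analysis.
- Rename the present set complete-case, say what a full round is, and keep the set as a sensitivity analysis.

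In 8.8, apply covariate-based deletion only to analyses that use the covariate concerned. Sections 5.3 and 5.4 can keep replacement, with replaced participants reported.

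The cost is SAP wording, plus a reason field on the case report form if it lacks one (the form is not among the documents). The downside is that the reported pass rate may be slightly lower.

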After five minutes, staff records whether an alert was triggered. Participant will remove brief ^d		X	
All participants will complete steps above. Only the first 22 participant will go on to complete the following steps.			

Participant applies new brief (study staff checks for correct application) and participant is in sitting position. ^a		X	
Study staff pours 360 mL saline into the brief and starts a timer for ten minutes. ^b		X	
After ten minutes, participant removes brief and gives it to the staff. ^c		X	
Staff weighs out at least 10.0 grams filter paper and records the weight. Staff places the filter paper centered on the wet brief and over the acquisition and dryness layer (ADL) places the calibrated weight on the filter paper and starts a timer for one minute.		X	
After one-minute, calibrated weight and filter paper is removed and the filter paper is weighed, and the weight is recorded.		X	
Study staff will complete steps below for all participants.			
Evaluation for adverse events	X	X	X
Participant dismissal			X
^a Study activity will occur after informed consent has been signed and the participant has met all the inclusion criteria and none of the exclusion criteria.			
^b This pour will only occur if the previous pour(s) did not trigger an alert. If the previous pour did trigger an alert the participant will either move to the application of the next brief or the participant will be dismissed if they are at the end of their participation.			
^c If the Pod alerts prior to the fourth pour, it is considered a pass. If it doesn't alert after five minutes post the third pour, it is a failure. Note: There is no minimum pour volume for the first alert.			
^d Whether there was an alert triggered or not, participant will either move to the application of the next brief or the participant will be dismissed if they are at the end of their participation.			
^e This step is part of the rewet testing. Only the first 22 participants enrolled in the study will perform the rewet testing.			

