6.4.2 Normal Saline Pours

Once the FitRight® System and tubing is properly setup on the participant, the study staff will pour 90 milliliters (mL) of normal saline (first pour) through the funnel system to enter the brief. Study staff will immediately start a calibrated timer for five minutes once the saline drains from the funnel system. After the five minutes, study staff will document whether the brief did or did not trigger an alert. If the brief triggers an alert, the brief passes and the participant is ready for the next brief. If the brief does not trigger an alert, study staff will pour an additional 150mL normal saline (second pour) through the funnel system and will immediately start a calibrated timer for five minutes once the saline drains from the funnel system.

After the five minutes, study staff will document whether the brief did or did not trigger an alert. If the brief triggers an alert, the brief passes and the participant is ready for the next brief. If the brief does not trigger an alert, study staff will pour an additional 120mL normal saline (third pour) through the filtration system and will immediately start a calibrated timer for five minutes once the saline drains from the funnel system.

After the five minutes, study staff will document whether the brief did or did not trigger an alert. If the brief triggers an alert, the brief passes and the participant is ready for the next brief. If the brief does not trigger an alert, the brief fails, and study staff will pour an additional 120mL normal saline (fourth pour) through the funnel system and will immediately start a calibrated timer for five minutes once the saline drains from the funnel system. After the five minutes, study staff will document whether the brief did or did not trigger an alert. No matter if the brief did or did not trigger an alert, the participant will move onto the next brief. The fourth pour, if required, will help to determine if more volume was needed to trigger the alert or if the system was defective.

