8.5 Endpoints

8.5.1. Primary Endpoint

FitRight® System alert value of pass (=1) or fail (=0), for each given value of fluid added (90, 150, 120, and 120 mL) and for each rotational position in the brief (sitting, laying supine, left side, and right side)

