8.5.3 Additional Endpoints

The percentage of pass alerts that were correctly triggered ((# passed/tests) x 100) and the percentage of failed alerts ((# fail/ # tests) x 100) will also be evaluated for the whole sample and stratified by volume of fluid and rotational position.

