8.9.1 Analysis of Primary Endpoints

The primary goal of this research study is to assess the reliability of the FitRight® Alert Indicator for the full sample and stratified by the four rotational positions, the three different fluid amounts,

and the combination of rotational positions and fluid amounts. Cronbach's coefficient alpha estimate's reliability by determining the internal consistency of a test or the average correlation of items within a test. The pass/fail values from this set of test runs will be compared to the derived variable of whether or not the test should have triggered an alert. Since the variables of interest are dichotomous (pass/fail), the coefficient alpha is equivalent to the Kuder-Richardson 20 (KR-20) reliability measure. It produces a correlation measure between 0 where a high KR20 coefficient (e.g., >0.90) is indicative of a homogeneous test. A reliability of 0.70 or higher for an acceptable rating and 0.80 or higher for a good rating.

In addition, a chi-square analysis will be conducted to determine if any association between rotational position and test status (pass/fail) exists. This analysis will be repeated to examine any possible associations between fluid added and test status (pass/fail).

Spearman correlation analysis will be used to examine possible associations between the key variables of triggered alert value (pass/fail), rotational position (sitting, supine, left side, right side), and fluid volume of 90 mL, 150 mL, 120 mL, and 120 mL with covariates of age, sex, and brief size. Additional t-tests or non-parametric tests will be employed to further examine any significant associations found in the correlational analyses between key and covariate measures.

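### The by-volume analyses ignore the stop-at-alert rule, so they describe only briefs that have not yet alerted and not how the device performs at each volume

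*Combined protocol and SAP*

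**What the plan says.** **Procedure.** Pours of 90, 150, 120 and 120 mL are given in sequence. Footnote b of the schedule in section 1.2 says of each later pour: "This pour will only occur if the previous pour(s) did not trigger an alert". Sections 4.1 and 6.4.2 repeat the rule. An alert by the reading after the third pour is a pass. Otherwise, section 6.4.2 says: "If the brief does not trigger an alert, the brief fails, and study staff will pour an additional 120mL normal saline (fourth pour". The fourth pour thus goes only to a brief that has already failed. Its stated purpose is to show whether more volume was needed or the product was defective.

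**Analysis.** Section 8.5.1 scores the primary endpoint as "pass (=1) or fail (=0), for each given value of fluid added (90, 150, 120, and 120 mL" and for each position. Section 8.5.3 defines "The percentage of pass alerts that were correctly triggered ((# passed/tests) x 100" and stratifies it by volume and position. Section 8.9.1 wants reliability "stratified by the four rotational positions, the three different fluid amounts" and by the two combined. After the chi-square of position against status it adds: "This analysis will be repeated to examine any possible associations between fluid added and test status (pass/fail".

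**Data sets.** Section 8.3 requires "full data on all covariates as well as the volume of fluid administered, the position, and whether or not the sensor triggered". Section 8.8 states that "listwise deletion will be used for the reliability analysis and chi-square analysis". No section says how a pour that was not given is coded, or what the denominator is for a percentage at a given volume.

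**The concern.** A skipped pour here is a sign of success. A brief that alerts at 90 mL has no second, third or fourth result because it worked. The by-volume outputs are written as if every brief were observed at every volume.

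Three things follow. First, the rate at the second or third pour is conditional on not having alerted earlier, and a reader will take it for the device's performance at that volume. Second, a single 120 mL stratum mixes third pours, where an alert is a pass, with fourth pours, where the brief has already failed. Third, the fluid-by-status chi-square compares groups that the stopping rule created, and it can count several pours of one brief as independent tests.

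At stake is how the study answers its primary question by volume: how much fluid the system needs before it alerts.

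**Working it through.** **Inputs from the documents.** 56 participants, so 56 briefs in the sitting position and 56 in the supine position. Planned success is around 90% (section 8.1). The pours are 90, 150, 120 and 120 mL, so the running totals are 90, 90 + 150 = 240, 240 + 120 = 360 and 360 + 120 = 480 mL.

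**Assumption.** The documents give no distribution of alerts over pours. I take one position with 50 of 56 briefs passing (89.3%, near the planned 90%), first alerts at pours one to three of a1 = 17, a2 = 17 and a3 = 16, and f = 6 failures. The plan gives no by-volume figure to reproduce.

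**Step 1: pours given.** The counts are 56, then 56 − a1 = 39, then 56 − a1 − a2 = 22, then f = 6. The total is 123.

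**Step 2: rate per pour against cumulative rate.**

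| Pour | Running total | Alerts / pours given | Cumulative alerts / all briefs |
|---|---|---|---|
| 1 | 90 mL | 17/56 = 30.4% | 17/56 = 30.4% |
| 2 | 240 mL | 17/39 = 43.6% | 34/56 = 60.7% |
| 3 | 360 mL | 16/22 = 72.7% | 50/56 = 89.3% |

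The two columns come from the same briefs. Only the last cumulative figure equals the brief-level pass rate.

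**Step 3: the shared 120 mL code.** Pooling pours three and four gives 22 + 6 = 28 pours. If no failed brief alerts at the fourth pour, the stratum shows 16/28 = 57.1%. If all six do, and an alert there is scored 1, it shows (16 + 6)/28 = 78.6%. The brief-level pass rate is 50/56 in both cases.

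**Step 4: fluid-by-status chi-square, using the plan's codes of 90, 150 and 120 mL.**
- One record per pour, no fourth-pour alerts: alerts 17, 17, 16 and non-alerts 39, 22, 12 give chi-square 5.76 on 2 df, p = 0.056.
- One record per pour, all six failed briefs alert at pour four: alerts 17, 17, 22 and non-alerts 39, 22, 6 give 17.6 on 2 df, p = 0.0002.
- One record per brief, coded by its last pass-eligible pour: passes 17, 17, 16 and fails 0, 0, 6 give 10.4 on 2 df. A fail can occur only in the 120 mL column, so the zeros are built in. All three expected fail counts are below 5 (1.82, 1.82, 2.36), so I quote no p-value.

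The pass rate of the briefs is the same in all three. The statistic moves with the layout and with what happens after a brief has already failed.

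**Step 5: listwise deletion, which depends on layout.** If the four pours are separate items, only briefs with all four results stay: f = 6 of 56, all failures, whatever the alert timing. With the first three pours as items, a3 + f = 22 of 56 stay, and 16/22 = 72.7% of these pass. With one record per pour given, a skipped pour makes no record and nothing is deleted.

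**The case against.** The strongest reply is that the plan is sound at brief level and can be read so that nothing is lost. Much of this stands.

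- **Section 8.3 does not exclude passing briefs.** It asks for the volume administered and whether the sensor triggered. A brief that alerts at 90 mL has both.
- **A reader might infer that listwise deletion discards the passing briefs.** The documents do not support that as stated. Section 8.6 collects volume and position as single categorical variables, which fits one record per observation, and then nothing is deleted. The loss in step 5 needs a separate-items layout that the plan does not describe.
- **A reader might infer that the headline pass percentage is ambiguous**, because 50 passing briefs of 56 could also be shown per pour given: 50/74 = 67.6% if every pass comes at pour one, 50/123 = 40.7% in the assumed split, 50/174 = 28.7% if every pass comes at pour three (no fourth-pour alerts). But sections 4.1 and 6.4.2 give a clear pass rule per brief, and section 8.9 asks for the key percentage for the full sample and by position, where that rule applies. Section 8.1 also speaks of brief tests. Only section 8.7 ties a test to a given volume.
- **A reader might infer that the volume chi-square is certain to be significant.** With running totals of 90, 240, 360 and 480 mL, passes 17, 17, 16, 0 and fails 0, 0, 0, 6 give chi-square 56 by construction. The plan does not code running totals, though, and sparse cells make the p-value from that table unreliable.

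None of this repairs the by-volume outputs. One record per pour avoids deletion but leaves the conditional denominators of step 2 and the pooled 120 mL stratum of step 3.

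**Conclusion.** The concern holds for the by-volume analyses in sections 8.5.1, 8.5.3 and 8.9.1. As written, they do not measure performance at each volume. In the assumed split the second-pour rate is 43.6%, where 60.7% of briefs have alerted by that volume; at the third pour the figures are 72.7% and 89.3%. Those sizes depend on the assumed 17/17/16 split and on 50 of 56 passing. The direction does not: once any brief has alerted early, the later denominators are a selected subset.

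The overall and by-position pass percentages are clear at brief level and are not in question. The deletion of passing briefs is conditional on layout and is a reason for one clarifying sentence, not a finding that data will be lost. The label of the analysis set, the requirement for complete covariates, and the derived variable in section 8.7, which is constant because every tested brief receives at least 90 mL, are separate points. The change should be made before analysis.

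**What to change.** Amend sections 8.5, 8.8 and 8.9.1 as follows.

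1. Define a test as one brief in one position, with pass meaning an alert by the third-pour reading, as sections 4.1 and 6.4.2 already have it.
2. By volume, report the cumulative percentage alerted by 90, 240 and 360 mL over all tested briefs in that position, each with a 95% confidence interval. A brief that has alerted stays counted as alerted.
3. Report the fourth pour (480 mL in total) separately, and never score it as a pass.
4. State that a pour not given after an alert is not missing data and does not trigger listwise deletion.
5. Replace the fluid-by-status chi-square and the by-volume KR-20 with the cumulative table.

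The cost is wording in three sections, with no added participants, pours or data. The volume chi-square and by-volume KR-20 are lost. The cumulative percentages share the same briefs, so they are descriptive and should not be tested against each other as independent groups.
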